### **12.2.5 Primary Analysis**

The primary endpoint is the change from baseline in the mean overall gum comfort questionnaire after 12 weeks of study. The subjects mean change from baseline for the Gum Comfort Questionnaire will be compared between groups using analysis of covariance (ANCOVA) and test between treatment groups at the 5% level of significance. The model will include the baseline value as covariate. Frequency distributions of the responses by treatment group will be provided to detail the whole range of responses. Within and between group estimates of treatment effects will be provided with 95% confidence intervals (CI's). The direction of the effect is anticipated in the direction of an improved gum comfort OHRQoL in favour of the experimental denture adhesive over the no adhesive group.

In the case of the assumptions underlying the model not being supported, a suitable transformation or non-parametric procedure will be used.

No imputation for missing values will be used.

The MITT population will be considered primary for this analysis. Analysis of the PP population (if applicable) will be secondary.

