1.4 Sample Size Calculation

The primary response variable is the change from baseline in the average of the 5 questions in The Gum Comfort Questionnaire at 12 weeks. There are no comparable data available for the consideration of the analysis of the responses to the Gum Comfort Questionnaire. However, similar questionnaires have been used and reported and the nature of the response variables using changes from baseline on a 5-point questionnaire allow us to predict the likely distributional aspects of such responses. From this exercise we can assume the standard deviation (SD) of the overall mean of gum comfort response can be represented by a Normal (0.8, 0.0862) random variable.

For a large number of simulated studies 100,000 the SD was sampled from this normal (prior) distribution. A clinically meaningful treatment effect was defined as -0.5 with adhesive vs no adhesive and was introduced into the simulated studies. With 57 evaluable subjects the power to detect such a difference with statistical significance (2-sided) at the 5% level was found to be 90%. This represents the average power to detect a mean difference of -0.5 between treatments over a plausible range (prior distribution) for the unknown SD and is often termed assurance.

In order to account for subject drop outs (assumed as 10%), 63 subjects per treatment arm should be randomized to ensure 57 subjects per arm are evaluable. The Modified Intent-to-Treat (MITT) population will be used for the primary analysis, and no correction to the alpha testing level will be made in respect of secondary endpoints.

2 Planned Analyses

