4.4.2.1 Statistical Hypothesis, Model, and Method of Analysis

Descriptive statistics (n, missing, mean, SD, SE, median, minimum and maximum) of the primary variable observed value will be provided ([Table 14.2.2.1](#)) at Baseline, Weeks 1, 4, 8 and 12, along with the change from baseline statistics at Weeks 1, 4, 8 and 12 by product group for the MITT population and ([Table 14.2.2.4](#)) for PP population.

Frequency distributions of the overall gum comfort score by product group will be provided displaying the complete range of responses from 0 – 20 at each week ([Table 14.2.2.2](#)) for MITT population.

The primary analysis is a comparison of the mean change from baseline in overall gum comfort score between Experimental Adhesive and No Adhesive at Week 12 for subjects eligible for the MITT population.

The null hypothesis for the primary endpoint is that the mean change from baseline in overall gum comfort score is equal between the 2 groups.

$$H_0: \mu_1 = \mu_2$$

The alternative hypothesis is that the mean change from baseline in overall gum comfort score is not equal between the 2 groups.

$$H_1: \mu_1 \neq \mu_2$$

The change from baseline in overall gum comfort score at Week 12 will be analysed using analysis of covariance (ANCOVA) with study product as a fixed effect and baseline overall gum comfort score as a covariate. Adjusted means and their SEs, 95% confidence intervals (CI), within treatment p-values for each product group will be displayed with product group difference, SE, 95% confidence interval of the difference and the between-treatment p-value in [Table 14.2.2.3](#) for MITT population and in [Table 14.2.2.5](#) for PP population. All statistical tests of hypotheses will be two-sided and will employ a level of significance of $\alpha = 0.05$.

This study will be considered successful if a statistically significant difference between the adjusted mean scores of the two product groups is observed to be in favor of the Experimental Adhesive.

The assumptions of the ANCOVA model i.e. normality of residual and equality of variances will be investigated. If the assumptions of the underlying model are violated, data transformations will be investigated and if suitable transformations cannot be found, an appropriate non-parametric test will be performed (e.g. Mann-Whitney U test).

All Gum Comfort Questionnaire responses with the overall and change from baseline scores will be listed ([Listing 16.2.6.1](#)).

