4.4.2.2 Supportive Analyses

If there is more than 10% difference in the overall number of subjects between PP and MITT populations, a summary of the primary efficacy variable will be presented for all subjects in the

PP population (Table 14.2.2.4) and the same ANCOVA model applied to the primary analysis will be performed on the PP population (Table 14.2.2.5).

Secondary efficacy variables are defined in Section 4.5.

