4.5.1 Efficacy (Secondary)

4.5.1.1 Overall Gum Comfort Score at Weeks 1, 4 and 8

Change from baseline in overall gum comfort questionnaire scores at Weeks 1, 4 and 8 (overall mean score) will be evaluated using the same model as used for primary efficacy analysis on the MITT population (Table 14.2.2.1).

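### The SAP judges success on the ANCOVA-adjusted mean difference but does not say whether the non-parametric fallback, if triggered, replaces ANCOVA for that decision

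*SAP*

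**What the plan says.** SAP 4.4.2.1 states the null hypothesis as equal mean change in overall gum comfort score and fits ANCOVA to the Week 12 change, with study product as fixed effect and baseline score as covariate. Table 14.2.2.3 is to show adjusted means, their difference, the 95% CI and the p-value. Success requires that "a statistically significant difference between the adjusted mean scores of the two product groups is observed to be in favor" of the adhesive.

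The same section then says that "normality of residual and equality of variances will be investigated". If the assumptions are violated, transformations are looked at first, and "if suitable transformations cannot be found, an appropriate non-parametric test will be performed (e.g. Mann-Whitney U test"). No test, cutoff or plot defines a violation or a suitable transformation. The variable to be tested or transformed is not named, and the success rule is not restated for this route.

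Protocol 12.2.5 has the same provision with no order of steps: "a suitable transformation or non-parametric procedure will be used". It also promises that "Within and between group estimates of treatment effects will be provided with 95% confidence intervals".

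Two other analyses depend on the primary model. In the per-protocol set, "the same ANCOVA model applied to the primary analysis will be performed on the PP population". Weeks 1, 4 and 8 are evaluated "using the same model as used for primary efficacy analysis on the MITT population", and Protocol 12.2.6 makes their analysis identical to that of Week 12.

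**The concern.** This is the trial's one confirmatory test. The hypothesis, the estimate, its interval and the success rule are all written for ANCOVA. The only test named for the last step of the fallback matches none of them: Mann-Whitney compares distributions by rank, has no adjusted means, and leaves out the baseline covariate. If it decides success, the rule in SAP 4.4.2.1 has nothing to act on, and the between-group estimate with 95% CI promised in Protocol 12.2.5 has no stated source.

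The timing adds to this. The residuals come from a model containing study product, and SAP 2.2 distributes the randomization codes only after database lock. The judgement that an assumption fails is therefore made unblinded, without a written criterion. A switch in either direction would be open to challenge.

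**Working it through.** **1. The plan's own figure.** Inputs from SAP 1.4 and Protocol 12.1: difference -0.5 on the 0-4 item-mean scale, SD from Normal(0.8, 0.0862), 57 evaluable per arm, two-sided 5%. The plan states: "With 57 evaluable subjects the power to detect such a difference with statistical significance (2-sided) at the 5% level was found to be 90" per cent.

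At a fixed SD of 0.8, SE = 0.8 × √(2/57) = 0.150, 0.5/0.150 = 3.34, and power = Φ(3.34 − 1.96) = 91.6%. Averaging two-sample t power over 100,000 SD draws, with 0.0862 read as an SD, gives 90.4%. The stated 90% reproduces, and it is the power of an unadjusted comparison of change.

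**2. What the covariate adds.** The baseline to Week 12 correlation ρ is not in the documents; 0.3, 0.5 and 0.7 are assumed. With equal variances, SD of change = σ√(2(1−ρ)) and ANCOVA residual SD = σ√(1−ρ²). Their ratio is √((1+ρ)/2).

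- ρ = 0.3: 0.8 × 0.806 = 0.645
- ρ = 0.5: 0.8 × 0.866 = 0.693
- ρ = 0.7: 0.8 × 0.922 = 0.738

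Averaged over the same SD prior, ANCOVA power is 97.8 / 96.1 / 94.0%.

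**3. Simulated power (%).** 57 per arm, difference -0.5, SD of change 0.8 before rounding, 4,000 trials per row (SE about 0.5 points near 90%). Grid means scores rounded to steps of 0.2 and clipped to 0-4; the baseline means are assumed. Rank ANCOVA is Quade's method.

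| Data | ρ | ANCOVA | t-test on change | Mann-Whitney on change | Rank ANCOVA |
|---|---|---|---|---|---|
| Normal | 0.3 | 98.3 | 90.4 | 89.4 | 98.1 |
| Normal | 0.5 | 96.3 | 91.0 | 89.0 | 95.7 |
| Normal | 0.7 | 94.6 | 91.6 | 90.0 | 92.0 |
| Grid, mean 2 | 0.3 | 98.2 | 89.8 | 88.1 | 97.6 |
| Grid, mean 2 | 0.5 | 96.4 | 90.2 | 88.9 | 95.3 |
| Grid, mean 2 | 0.7 | 93.6 | 89.9 | 88.4 | 92.2 |
| Grid, mean 1 | 0.3 | 98.1 | 86.8 | 85.1 | 97.8 |
| Grid, mean 1 | 0.5 | 95.2 | 84.8 | 82.7 | 94.6 |
| Grid, mean 1 | 0.7 | 90.8 | 82.8 | 79.8 | 90.3 |

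Mann-Whitney trails ANCOVA by 5 to 13 points here. It trails the t-test on change by only 1 to 3, so most of the loss is the covariate, not the use of ranks. Rank ANCOVA trails ANCOVA by 0.2 to 1.4 points, except 2.6 on normal data at ρ = 0.7.

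Simulating five 0-4 items directly (SD of change 0.80, difference -0.5, baseline item mean 0.8 to 2.0) gave a gap of 6 to 10 points. Another set of assumed five-item inputs put it as high as 19.

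**4. Type I error.** ANCOVA 4.6-5.4% across the settings run; Mann-Whitney 4.6-5.7%; rank ANCOVA 4.8-5.5%.

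**5. How often the fallback is reached.** The five-item data were run through an assumed rule: Shapiro-Wilk or Brown-Forsythe on the ANCOVA residuals below a cutoff, then square root, then log, then Mann-Whitney. Ranges cover two assumed correlations.

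| Baseline item mean | Reached, 5% cutoff | Average power loss | Reached, 1% cutoff | Average power loss |
|---|---|---|---|---|
| 0.8 | 45-71% | 5-6 points | 17-40% | 2-3 points |
| 1.2 | 15-43% | 1-4 | 2-9% | 0-0.7 |
| 1.6 | 14% | 1 | 2% | 0.1-0.2 |
| 2.0 | 6-8% | 0.5 | 0.5-1% | 0.1 |

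Among trials that reached Mann-Whitney at the 5% cutoff, 6-12% had a significant ANCOVA and a failed rank test; the reverse occurred in about 1% or fewer. Type I error of the whole rule was 4.7-5.9%.

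**The case against.** The strongest reply is that SAP 4.4.2.1 can be read so that no conflict arises. ANCOVA is prescribed without condition, its table is specified, success is tied to adjusted means, and the fallback is only to be performed; nothing there says that it replaces ANCOVA. That reading is tenable, and on it the estimate and CI do have a source. But Protocol 12.2.5 says the alternative will be used where the model is not supported, and no passage settles the matter. The embedded list of data displays might, but it cannot be read here.

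Other parts of the reply stand and limit the point:

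- Mann-Whitney is the third step and only an example, so a baseline-adjusted rank test is already permitted, though not specified.
- A reader might infer that baseline is discarded altogether. It is not: the endpoint remains change from baseline, and only the covariate is lost.
- A reader might infer that Weeks 1, 4 and 8 are left open. Protocol 12.2.6 ties them to the primary analysis, so they inherit the same ambiguity rather than adding a new one.
- Table 5-1 is not at fault. The protocol already contains the fallback, so there was no change to record.
- The frequencies in step 5 rest on an assumed rule and assumed baselines. The SAP says only that assumptions will be investigated, which could mean looking at plots.

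**Conclusion.** The point holds as a gap in the primary analysis: the plan does not say which result decides success once the fallback is triggered. If the fallback replaces ANCOVA, the success rule has no meaning and the estimate with its CI has no stated source.

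Under the assumed distributions, with 57 per arm, the unadjusted rank test costs roughly 5 to 19 points of power against ANCOVA whenever it decides the trial. The average cost over trials is smaller and may be negligible if baseline scores lie mid-scale. The switch protects little, because ANCOVA held about 5% type I error in the bounded-score settings.

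Two stronger readings are not supported. A reader might infer that the sample size is wrong; the 90% reproduces and matches an unadjusted comparison, so what is lost is mainly the gain from adjustment. In the assumed floor-effect setting Mann-Whitney falls to 80-85%, but the unadjusted t-test falls too, to 83-87%. A reader might also infer an inflated false-positive rate; under a mechanical rule it stayed at 4.7-5.9%, and the simulations say nothing about a judgement made case by case.

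This should be corrected before unblinding; it does not invalidate the design.

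**What to change.** - In SAP 4.4.2.1, state that success is judged only on the baseline-adjusted ANCOVA difference and its 95% CI, whatever the residual checks show.
- Replace the Mann-Whitney example with one named baseline-adjusted rank analysis, as a sensitivity analysis. Rank ANCOVA (Quade) would serve: regress Week 12 ranks on baseline ranks and compare the residuals between arms.
- State that Weeks 1, 4 and 8 follow the same rule, consistent with Protocol 12.2.6 and SAP 4.5.1.1.
- The hypothesis-generating scores (OHIP-Edent, GOHAI and the single Gum Comfort items in SAP 4.5.1.2) may keep a non-parametric alternative, preferably the same rank test.
- Record the resulting change from Protocol 12.2.5 in Table 5-1.

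The cost is a short SAP edit, a few lines of code and one table entry; conduct, data collection and sample size are untouched. The downside is that a rank result can no longer serve as the primary test if residuals are clearly non-normal.

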4.4.2.2 Supportive Analyses

If there is more than 10% difference in the overall number of subjects between PP and MITT populations, a summary of the primary efficacy variable will be presented for all subjects in the

PP population (Table 14.2.2.4) and the same ANCOVA model applied to the primary analysis will be performed on the PP population (Table 14.2.2.5).

Secondary efficacy variables are defined in Section 4.5.

4.4.3 Handling of Missing Values/Censoring/Discontinuations

Subjects who withdraw from the study prematurely will be included in the statistical analyses up to the point of discontinuation.

4.4.3.1 Handling of Missing Values in Questionnaire Data

For any overall questionnaire score (with the exception of product sensory questionnaire) or functional domain score (where applicable), if there are $\leq 20\%$ of missing values/scores that are required for the derivation of the overall or functional domain score, the missing score will be imputed pro-rated. If there is $> 20\%$ of missing values, the score will be set to missing.

This $\leq 20\%$ imputation rule will therefore be dependent on the number of questions per functional domain or overall score. For example:

Number of Questions within Domain or Overall Score	Number of Scores Missing	Impute or Set to Missing
1 to 4	≥ 1	Set to missing
5 to 9	1	Impute
	≥ 1	Set to missing
10 to 15	1	Impute
	2	Impute
	≥ 2	Set to missing
16 to 19	1	Impute
	2	Impute
	3	Impute
	≥ 4	Set to missing

Scores will be imputed using the following calculation:

$$\text{Imputation score} = s \cdot n / (n - m)$$

Where:

s = total value of scores available

n = number of questions within the overall score or domain

m = number of missing values

Imputation examples are provided for a couple of the questionnaires below

Gum-Comfort Questionnaire

Gum-comfort questionnaire comprises of 5 questions; if 1 of the scores out of the 5 questions is missing, the overall gum comfort score will be derived as:

Question	Response
1) My gums feel comfortable when wearing my denture(s)	1
2) I feel my gums are cushioned from the impact of chewing and biting	2
3) My gums do not feel sore at the end of the day	3
4) My gums are not irritated by trapped food particles under my denture(s)	3
5) My gums do not feel tired at the end of the day	missing

Rating scale: [0] - Agree Strongly, [1] - Agree Somewhat, [2]- Neither Agree or Disagree, [3]- Disagree Somewhat, [4]- Disagree Strongly

Imputation of Overall score for above example: $(1+2+3+3)*5/4 = 11.25$

OHIP-Edent Questionnaire

OHIP-Edent Questionnaire comprises of 19 questions grouped into 6 functional domains (see section 4.5.1.4 for further details):

Domain	Question	Number of Questions within Domain	Response	Total Score
Functional limitations	1-3	3		missing
	1) Have you had difficulty chewing any foods because of problems with your teeth, mouth or dentures?		1	
	2) Have you had difficulty with food catching in your teeth or dentures?		2	
	3) Have you felt that your dentures have not been fitting properly?		missing	
Physical pain	4-7	4		missing
	4) Have you had painful aching in your mouth?		missing	
	5) Have you found it uncomfortable to eat any foods because of problems with your teeth, mouth or dentures?		1	
	6) Have you had sore spots in your mouth?		3	
	7) Have you had uncomfortable dentures?		2	
Psychological discomfort	8-9	2		3
	8) Have you been worried by dental problems?		1	
	9) Have you been self-conscious because of your teeth, mouth or dentures?		2	

Physical disability	10-12	3		4
10) Have you had to avoid eating some foods because of problems with your teeth mouth or dentures?			1	
11) Have you had to interrupt meals because of problems with your teeth, mouth or dentures?			3	
12) Have you been unable to eat because of problems with your teeth, mouth or dentures?			0	
Psychological disability	13-14	2		4
13) Have you been upset because of problems with your teeth, mouth or dentures?			1	
14) Have you been a bit embarrassed because of your teeth, mouth or dentures?			3	
Social disability	15-19	5		8.75
15) Have you had difficulty with being less tolerant of your spouse or family because of problems with your teeth, mouth or dentures?			1	
16) Have you been a bit irritable with other people because of problems with your teeth, mouth or dentures?			missing	
17) Have you avoided going out because of problems with your teeth, mouth or dentures?			2	
18) Have you been unable to enjoy other people's company as much because of problems with your teeth, mouth or dentures?			2	
19) Have you felt that life in general was less satisfying because of problems with your teeth, mouth or dentures?			2	
Overall OHIP-Edent score	1-19	19	27	32.06

Rating Scale: [0] Never [1] Rarely [2] Occasionally [3] Often [4] Very Often

For the overall OHIP-Edent score is calculated as:

$$27 * 19 / 16 = 32.06$$

Where 16 (19-3) is the denominator due to the 3 missing scores in questions 3, 4 and 16.

Product Sensory Questionnaire

There will be no imputation of the product sensory score which comprises of 6 questions (see section 4.5.1.6 for further details). If one of more of the question scores is missing, then the product sensory score will be set to missing.

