### **12.2.8 Handling of Dropouts and Missing Data**

Missing data will not be replaced or imputed. Dropouts will be included in analyses up to the last assessments at the point of discontinuation.

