4.4 Analysis of Efficacy

4.4.1 Primary Efficacy Endpoint

4.4.2 Primary Efficacy Endpoint Definition

The primary endpoint is the change from baseline in the mean overall gum comfort questionnaire score after 12 weeks of study.

The gum-comfort questionnaire is comprised of 5 questions that record the subject-perceived comfort of their denture-bearing tissues. The questions have 5 possible responses (Agree Strongly, Agree Somewhat, Neither Agree or Disagree, Disagree Somewhat, Disagree Strongly) and are scored on a 0 (Agree Strongly) to 4 (Disagree Strongly) scale for all questions. The score from all 5 questions will be summed as the overall gum comfort score at each time point, which will have a range score of 0-20 where a low score is more favorable. See section 4.4.4.1 on how to deal with missing scores.

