4.7 Other Analysis

In addition to what was planned in the protocol, Cronbach's coefficient alpha will be calculated at Week 1, 4, 8 and 12 for OHIP-Edent domains ([Table 14.2.5.5](#)) and GOHAI domains ([Table 14.2.6.5](#)).

Cronbach's coefficient alpha is a measure of internal consistency, that is, how closely related a set of items are as a group. It is considered to be a measure of scale reliability which can be used to support the use of combined domain scales.

Cronbach's Coefficient will be calculated as:

$$\alpha = \left(\frac{k}{k-1} \right) \left(1 - \frac{\sum_{i=1}^k \sigma_{y_i}^2}{\sigma_x^2} \right)$$

... where: k refers to the number of scale items

$\sigma_{y_i}^2$ refers to the variance associated with item i

σ_x^2 refers to the variance associated with the observed total scores

A coefficient of 0.7 and above shows that the internal consistency/reliability between the domain is at least acceptable.

5 Changes to the Protocol Defined Statistical Analysis Plan

Any changes from the originally planned statistical analysis specified in the protocol are outlined in [Table 5-1](#).

Table 5-1 Changes to Protocol Defined Analysis Plan

Table	Reporting & Analysis Plan	
Statistical Analysis section	Statistical Analysis Plan	Rationale for Changes

Section 12.2.1 Definition of Analysis Population
 
The per protocol (PP) population includes all MITT subjects who fully comply with all study procedures and restrictions. Deviations will be determined and applied prior to unblinding and consist of variations in criteria likely to affect the interpretation of the efficacy parameters.
	
Section 4.1.3 Analysis Population
 
PP population includes all subjects in MITT population who comply with all study procedures and restrictions that may affect the interpretation of the primary response. Deviations will be determined and applied prior to unblinding and consist of variations in criteria likely to affect the interpretation of the efficacy parameters.
	
To provide clarification of the definition.

Details were not included
	
Section 4.7 Other Analysis
 
Cronbach coefficient alpha will be derived for OHIP-EDENT domains and GOHAI domains.
	
Cronbach's coefficient alpha is a measure of internal consistency, that is, how closely related a set of items are as a group. It is considered to be a measure of scale reliability which can be used to support the use of combined domain scales.

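### The item-missing rule for the primary Gum Comfort score contradicts itself and, undeclared, the protocol; no analysis tests the loss of subjects without Week 12 data

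*SAP*

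**What the plan says.** **Missing items.** SAP 4.4.3.1 pro-rates a total or domain score if no more than 20% of its items are missing; above that, the score is missing. The formula is s·n/(n − m), where s is the sum of the answered items, n the number of items and m the number missing. For Gum Comfort it states that "if 1 of the scores out of the 5 questions is missing, the overall gum comfort score will be derived as" (1+2+3+3)×5/4 = 11.25. The table in the same section reads:

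- 5 to 9 items: impute at 1 missing; set to missing at ≥1.
- 10 to 15 items: impute at 1 or 2 missing; set to missing at ≥2.

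SAP 4.4.2 sends the reader to a different place for the rule: "See section 4.4.4.1 on how to deal with missing scores".

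**Protocol rule.** Protocol 12.2.5, on the primary analysis: "No imputation for missing values will be used". Protocol 12.2.8: "Missing data will not be replaced or imputed". SAP section 5 introduces Table 5-1 with "Any changes from the originally planned statistical analysis specified in the protocol are outlined in" it. The table lists only the per-protocol (PP) definition and Cronbach's alpha.

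**Missing visits.** For MITT, SAP 4.1.3 asks for one post-randomization Gum Comfort score at any visit. The primary model in SAP 4.4.2.1 uses Week 12 change only, with product as factor and baseline as covariate. The one supportive analysis (SAP 4.4.2.2) repeats that model in the PP population, and only on a condition: "If there is more than 10% difference in the overall number of subjects between PP and MITT populations".

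**The concern.** The derivation of the primary score should have one reading. As printed, a subject with four of five Gum Comfort answers is both scored and set to missing. The protocol bars imputation without exception and the SAP itself calls pro-rating imputation, so a reader of Table 5-1 would not learn that the primary score is handled differently from the protocol.

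The visit-level gap is the inferential one. A subject with scores at Weeks 1, 4 or 8 but not Week 12 belongs to MITT and adds nothing to the primary test. Subjects know their arm and rate the endpoint themselves, so leaving could be related to perceived benefit, and differently so in the two arms. PP is a subset of MITT, so the PP analysis can only remove more subjects.

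**Working it through.** **1. The SAP's own examples.** Gum Comfort: 9×5/4 = 11.25. OHIP-Edent Social disability: (1+2+2+2)×5/4 = 8.75. OHIP-Edent total: 27×19/16 = 32.06. All reproduce, and all follow the 20% prose.

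**2. Prose against table, for the 12 total and domain scores (1 Gum Comfort, 7 OHIP-Edent, 4 GOHAI).**

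| Score | Items | Prose rule | Table | Agree |
|---|---|---|---|---|
| Gum Comfort total; OHIP-Edent Social disability; GOHAI Psychosocial | 5 | 1/5 = 20.0%: impute; 2/5 = 40%: missing | 1 impute, ≥1 missing | No |
| GOHAI total | 12 | 2/12 = 16.7%: impute; 3/12 = 25%: missing | 2 impute, ≥2 missing | No |
| OHIP-Edent total | 19 | 3/19 = 15.8%: impute; 4/19 = 21.1%: missing | 3 impute, ≥4 missing | Yes |
| OHIP-Edent Physical pain; GOHAI Functional | 4 | 1/4 = 25%: missing | ≥1 missing | Yes |
| OHIP-Edent Functional limitations and Physical disability; GOHAI Pain/Discomfort | 3 | 1/3 = 33.3%: missing | ≥1 missing | Yes |
| OHIP-Edent Psychological discomfort and Psychological disability | 2 | 1/2 = 50%: missing | ≥1 missing | Yes |

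Four scores conflict and eight agree.

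**3. Item-level size.** The documents give no item non-response rate, so no number of subjects can be claimed. As a scale: the plan's 90% assurance reproduces as 90.4% (57 per arm, difference 0.5, two-sided 5% t-test averaged over SD ~ Normal(0.8, 0.0862)). If the set-to-missing line were programmed and an assumed 2%, 5% or 10% of the 57 per arm were lost to it, assurance would be 89.9%, 89.0% or 87.4%.

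**4. Visit-level size.** At the planned 10% dropout, 63×0.9 = 56.7, so about 6 of 63 per arm lack a Week 12 score. The documents give no rate by arm and no mechanism; the rest of this step is assumed.

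- Setup: 63 per arm, 0–4 mean-item scale, SD of change 0.8, correlation 0.6 between any two visits, 4,000 trials per scenario, true effect 0 or −0.5, dropout after Week 4.
- Standard error: SD of change 0.8 gives 0.64 = 2σ²(1−0.6), so σ² = 0.80. Residual variance after baseline adjustment is 0.80×(1−0.36) = 0.512. SE = √0.512 × √(2/57) = 0.134; the simulation gave about 0.135.
- Dropout odds rise 1.6, 2.7 or 7.4 times per SD of worse Week 4 change (logistic slopes 0.5, 1, 2).

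| Dropout, adhesive vs control | Bias of Week 12 ANCOVA |
|---|---|
| 10% vs 10% | within 0.004 of zero |
| 15% vs 5% | −0.010 to −0.035 |
| 5% vs 15% | +0.010 to +0.034 |
| 18% vs 2% | −0.019 to −0.052 |

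Negative values favour the adhesive. In SE units the unequal cases run from 0.010/0.135 = 0.1 to 0.052/0.135 = 0.4. The false-positive rate was 5.1% to 6.2%. Regression on baseline, Week 1 and Week 4, averaged over all subjects, left bias within 0.005. Repeating the simulation moved the biases by at most about 0.005 and put the false-positive rate at 4.5% to 6.7%.

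If dropout depends instead on the unobserved Week 12 score (15% vs 5%, true effect 0), bias is −0.032 to −0.080, and using earlier visits leaves −0.027 to −0.065, roughly 80% of it. At −0.080 the shift is 0.080/0.135 = 0.59 SE, which gives a false-positive rate of about 9% by normal approximation.

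On the 0–20 sum that the SAP analyses, multiply biases and SE by 5; the ratios do not change.

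**5. How far off the missing subjects would have to be.** With SD 0.8 and 63 per arm, the critical difference is 1.979×0.8×√(2/63) = 0.282. If 6 of 63 adhesive subjects are missing, significance is lost when they average (observed difference − 0.282)/(6/63) points worse than adhesive completers: 0.19 for an observed −0.30, 0.71 for −0.35, 1.24 for −0.40 and 2.29 for −0.50. Only a borderline result is fragile.

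**The case against.** - **The table is a drafting slip that the section itself resolves.** The prose states the rule, the table is offered as an example, and two worked five-item examples apply the prose. A symbol misread when the PDF was converted to text cannot be excluded either, although the same sign makes sense in the 1–4 and 16–19 item rows. This stands as to intent, and it limits the weight. It does not remove two opposite outcomes printed for the primary score.
- **Few items may be missing.** Protocol 9.2.1 has ambiguous answers clarified before the subject leaves, and 11.3 has staff and monitor review the questionnaires. This stands.
- **Pro-rating is scoring, not imputation.** Protocol 12.1 defines the response as the average of five questions, and s·n/(n − m) is the average of the answered items put back on the sum scale. That is arguable, but the SAP uses the word imputation and the protocol makes no exception. One line in Table 5-1 settles it.
- **The visit-level bias is small, assumed, and least curable where it is largest.** This stands. A repeated-measures model removes bias explained by observed scores and little of the rest.
- **Dropout will be visible anyway.** The SAP tabulates missing counts by week, discontinuation reasons by group, and ANCOVA at Weeks 1, 4 and 8. These would show uneven loss. None of them re-estimates the Week 12 difference with the lost subjects included.

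**Conclusion.** All three parts hold. The table contradicts its own rule for 4 of 12 scores, including the primary; the intent is recoverable, so this is a correction to make before programming and not a threat to the trial. The pro-rating is an undeclared departure from the protocol. The Week 12 ANCOVA drops MITT subjects with no Week 12 score, and nothing planned tests the effect.

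The likely size is modest: near zero with equal dropout, 0.1 to 0.4 SE with unequal dropout driven by observed scores, and up to 0.6 SE (0.080/0.135) if driven by the unobserved Week 12 score. These sizes rest on the assumed arm-specific rates, slopes and correlation. The documents supply only a single 10% rate, and bias needs dropout that is both outcome-related and different between arms. Because subjects know their arm, that cannot be excluded in advance.

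**What to change.** 1. In the SAP 4.4.3.1 table, set to missing at ≥2 for 5–9 items and at ≥3 for 10–15 items. Three of 15 is exactly 20%, so relabelling the rows 10–14 and 15–19 would make the table exact; no score here has 15 items.
2. Point SAP 4.4.2 to 4.4.3.1.
3. List item pro-rating in Table 5-1 as a departure from Protocol 12.2.5 and 12.2.8.
4. Keep the Week 12 ANCOVA as primary. Pre-specify one sensitivity analysis in MITT: a repeated-measures model for change at Weeks 1, 4, 8 and 12 with product, visit, product-by-visit, baseline and baseline-by-visit, unstructured covariance, and the Week 12 contrast. State that it corrects only for dropout explained by observed scores.

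The cost is two table cells, one cross-reference, one change-log entry and one extra model. No new data are needed, and the primary analysis and sample size do not change.
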